2.4 Endpoints

2.4.1 Primary Endpoint

- Median TTP will be calculated in months from date of first dose of protocol therapy to date of removal from study for progression. For patients removed from study for other reasons than progression (such as toxicity, withdrawal of consent, death without documented progression, or other reasons without clinical or radiographic evidence of tumor progression), TTP will be censored at the date last known to be progression-free.

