6.1.4 End-of-Treatment Study Procedures (within 60 days)

End-of-Treatment is defined as the day on which a decision is made by an investigator to discontinue a patient's participation in the study, often due to disease progression or toxicity, or by a patient to withdraw consent; this may also be referred to as the last day on study and may not necessarily coincide with the last day of protocol therapy, particularly if study drug has been held for toxicity.

- Complete physical examination, including height and weight measurement
- Vital signs, including temperature, blood pressure, heart rate, pain score, and oxygen saturation
- Update medical history
- Evaluation of clinical response or deterioration
- Evaluation of adverse events
- Concomitant medications
- ECOG Performance Status
- Child-Pugh class assessment
- Safety laboratory assessments: CBC w/ Diff, complete metabolic panel (electrolytes, BUN, creatinine, glucose, calcium, magnesium, phosphorus, total bilirubin, direct bilirubin, alkaline phosphatase, albumin, AST, and ALT), INR; serum AFP and HBV DNA quantitative by PCR should be measured if not done within 4 weeks
- If not done within preceding 8 weeks, imaging with CT chest (with or without contrast) plus triphasic CT abdomen and pelvis with intravenous contrast or triphasic gadolinium-enhanced MRI abdomen/pelvis to assess sites of known tumor using RECIST 1.1 measurements and to monitor for lung toxicity
- Banking of blood specimens if >4 weeks since specimens collected for banking

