6.1.6 Long Term/Survival Follow-up Procedures

Patients will be followed every 3-6 months (\pm 3 months) for up to 5 years after study discontinuation or until death, whichever comes first.

The following procedures will be performed at standard-of-care clinic visits with treating investigator or by telephone calls from treating investigator or a designated study coordinator (\pm 2 months):

- Evaluation of clinical response or deterioration.
- Overall survival will be measured from time of first dose of protocol therapy to date of death; for patients who are lost to follow up, survival will be censored at date last known to be alive.
- Evaluation of any residual symptomatic adverse events (if applicable).
- Other anti-cancer therapies.

Table 6.1 Schedule of Study Procedures and Assessments

Period/Procedure	Screening	Cycle 1				Cycle 2 and future Cycles				End of Treatment visit	Follow Up Visit*
Study Day/Visit Day	-28 to 1	1	8	15	22	1	8	15	22		
Informed consent	X										
Archival Specimen Collection ¹	X										
AE assessment		X	X	X	X	X				X	X
Concomitant medications	X ²	X	X	X	X	X				X	
Treatment/Drug Administration											
Temsirolimus ¹⁷		X	X	X	X	X	X	X	X		
Sorafenib ³		X	X	X	X	X	X	X	X		
Clinical procedures											
Physical exam	X	X	X	X	X	X				X	
Vital signs	X	X	X	X	X	X	X ⁴	X	X	X	
Medical history	X									X	X ⁶
Liver disease assessment ⁵	X										
Performance Status	X					X				X	
Laboratory procedures											
Hematology (CBC w/Diff)	X	X	X	X	X	X	X	X	X	X	
Blood chemistry ⁷	X	X	X	X	X	X	X	X	X	X	
Coagulation ⁸	X	X	X	X	X	X	X	X	X	X	
AFP		X				X				X	
HCV, HBV sAb, HBV sAg, HBV cAb total & IgM ¹⁶	X										
Hemoglobin A1c	X										
Hepatitis B viral DNA quantitative by PCR ⁹	X ⁹					X ⁹				X ⁹	
Fasting total cholesterol, triglycerides, and blood glucose ¹⁰	X ¹⁰					X ¹⁰					

Table 6.1 Schedule of Study Procedures and Assessments

Period/Procedure	Screening	Cycle 1				Cycle 2 and future Cycles				End of Treatment visit	Follow Up Visit*
Study Day/Visit Day	-28 to 1	1	8	15	22	1	8	15	22		
Standing phosphate repletion ¹¹	X ¹¹	X ¹¹				X ¹¹					
CTC ¹²		X ¹²				X ¹²					
Banking blood samples ¹³		X ¹³	X ¹³			X ¹³				X ¹³	
Pregnancy test (HCG)	X										
Imaging procedures											
Imaging (CT or MRI)	X					X ¹⁴				X ¹⁵	

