7.1.2 Time to Event Endpoints

Time to Progression (TTP)

TTP is defined as the duration from date of first dose of protocol therapy to date of removal from study for radiographic (per RECIST 1.1) and/or clinical progression including death attributed to progression. For patients removed from study for other reasons than progression (such as toxicity, withdrawal of consent, death without documented progression, or other reasons without clinical or radiographic evidence of tumor progression), TTP will be censored at the date of study discontinuation.

Time to Treatment Failure (TTF)

TTF will be measured from date of first dose of protocol therapy to date of study discontinuation for progression, death, or toxicity. For patients removed from study for other reasons (such as noncompliance or withdrawal of consent), TTF will be censored at the date of study discontinuation.

Progression-Free Survival

Progression-free survival (PFS) is defined as the duration of time from date of first dose of protocol therapy to time of documented radiographic and/or clinical disease progression or death from any cause. Patients who have not progressed or died are censored at the date last known to be progression-free.

Overall Survival (OS)

Median OS for all enrolled patients who receive at least one dose of protocol therapy will be calculated from date of first dose of protocol therapy until date of death, using chart review and/or follow up phone calls to determine date of death in patients after removal from study. The survival of patients still alive after 5 years of follow up post study discontinuation will be censored. Alive patients are censored at the date last known alive.

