9.1.2 Primary Endpoint

Median TTP will be calculated in months from date of first dose of protocol therapy to date of removal from study for radiographic (per RECIST 1.1) and/or clinical progression including death attributed to progression. For patients removed from study for other reasons than progression (such as toxicity, withdrawal of consent, or death from other causes than documented radiographic and/or clinical progression), TTP will be censored at the date last known to be progression-free.

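### Read literally, section 9.1.2 does not count progression found on the end-of-treatment scan when the recorded reason for removal is toxicity or withdrawal, and the plan's TTP and PFS definitions disagree on this case

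*Combined protocol and SAP*

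**What the plan says.** **TTP, section 9.1.2.** The event date is the "date of removal from study for radiographic (per RECIST 1.1) and/or clinical progression including death attributed to progression". The censoring sentence opens "For patients removed from study for other reasons than progression (such as toxicity, withdrawal of consent" and goes on to deaths from other causes; for all of these, "TTP will be censored at the date last known to be progression-free".

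**TTP, section 2.4.1.** The event is again removal for progression. The list of censoring reasons, however, ends with "other reasons without clinical or radiographic evidence of tumor progression), TTP will be censored at the date last known to be progression-free".

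**TTP, section 7.1.2.** The event clause matches 9.1.2 and the same qualifier about absence of progression appears, but the date differs: "TTP will be censored at the date of study discontinuation".

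**End-of-treatment scan, section 6.1.4.** End of treatment is the day someone decides to stop participation; progression, toxicity and withdrawal of consent are all mentioned. Procedures carry a 60-day window. The scan is conditional: "If not done within preceding 8 weeks, imaging with CT chest (with or without contrast" and abdomen/pelvis is done with RECIST 1.1 measurement. On-study scans are every 8 weeks, plus or minus 7 days (Table 6.1).

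**PFS.** Section 2.4.2 dates the event at documented progression or death, but its censoring sentence refers to the reason for removal. Section 7.1.2 censors only patients who have neither progressed nor died. Section 9.1.3 dates the event at study removal for progression or death.

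**The concern.** The decision to stop treatment, and the reason recorded for it, can precede the end-of-treatment scan. A patient stopped for toxicity may then have RECIST progression documented on a protocol scan. Under 9.1.2 as written, the recorded reason decides the matter: there is no event, and follow-up ends before the scan that showed progression.

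Independence of removal and progression cannot be taken for granted. Stopping either drug removes the patient (sections 5.2 and 5.3), and several removal triggers in section 5.2.3 are hepatic, such as Grade 4 bilirubin or ascites. In hepatocellular carcinoma these may accompany tumour growth. The trial is open-label, so the reason for removal is an investigator's judgement. It has no control arm in which an upward shift could cancel, and section 9.2.1 ties the next step to a median TTP above 6 months.

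**Working it through.** **1. The plan's own figure.** Exponential medians of 3 and 6 months give 6-month rates of 0.5^(6/3) = 0.25 and 0.5^(6/6) = 0.50, as in section 9.2.1. For an exact binomial test with N = 25, requiring at least 10 patients progression-free at 6 months gives one-sided alpha 0.071 and power 0.885. Requiring at least 9 gives alpha 0.149, above the 10% limit. The stated 88% is reproduced, and nothing in this point changes it.

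**2. One patient under each definition.** Take a patient removed for toxicity whose end-of-treatment scan shows RECIST progression.

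| Section | Endpoint | Result |
|---|---|---|
| 9.1.2 | TTP | Not an event; censored at date last known progression-free |
| 2.4.1 | TTP | Same, unless the qualifier governs the whole list; then the censoring clause does not reach the patient |
| 7.1.2 | TTP | Same ambiguity; if censored, at study discontinuation |
| 2.4.2 | PFS | Event clause is met; censoring sentence points the other way |
| 7.1.2 | PFS | Event |
| 9.1.3 | PFS | Not an event; censored |

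No section addresses the end-of-treatment scan expressly.

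**3. Size.** The documents give no rate of removal for reasons other than progression, so this is assumed. Settings: exponential TTP; scans every 8 weeks; end-of-treatment visit uniform over 0 to 60 days after the decision (6.1.4 does not state the direction of its window); scan only if the last was more than 8 weeks before; 400,000 simulated patients per scenario. The removal parameter is 10, 20 or 30%. Removals actually occurring before detected progression were 11 to 37% in the independent scenarios and 8 to 24% in the clustered ones. Clustered means that the removed patients leave within 4 weeks after true progression.

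| Removal | True median | Parameter | Progressions at end of treatment per 25 | 6-month KM rate, 9.1.2 | Rate if counted | Difference (points) |
|---|---|---|---|---|---|---|
| Independent | 3 | 10% | 0.7 | 0.279 | 0.275 | 0.4 |
| | 3 | 20% | 1.3 | 0.281 | 0.270 | 1.1 |
| | 3 | 30% | 2.0 | 0.284 | 0.264 | 2.0 |
| | 6 | 10% | 0.4 | 0.530 | 0.527 | 0.3 |
| | 6 | 20% | 0.7 | 0.531 | 0.524 | 0.7 |
| | 6 | 30% | 1.1 | 0.532 | 0.519 | 1.3 |
| Clustered | 3 | 10% | 1.2 | 0.298 | 0.291 | 0.7 |
| | 3 | 20% | 2.3 | 0.320 | 0.303 | 1.7 |
| | 3 | 30% | 3.5 | 0.347 | 0.318 | 2.9 |
| | 6 | 10% | 1.1 | 0.551 | 0.541 | 1.0 |
| | 6 | 20% | 2.3 | 0.576 | 0.555 | 2.1 |
| | 6 | 30% | 3.4 | 0.598 | 0.566 | 3.2 |

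**4. What is bias and what is extra detection.** With 8-weekly scans and no removals, a patient is progression-free at 6 months if true progression comes after week 24. At 4.348 weeks per month the rate is 0.5^(24/13.04) = 0.279 for median 3 and 0.5^(24/26.09) = 0.529 for median 6. Against that benchmark, 9.1.2 under independence is high by at most 0.284 - 0.279 = 0.5 points and 0.532 - 0.529 = 0.3 points, so it is nearly unbiased; most of the gap there is the additional scan finding progression sooner. Under clustering at 30%, 9.1.2 is high by 0.347 - 0.279 = 6.8 points and 0.598 - 0.529 = 6.9 points. Counting the conditional scan removes 2.9 and 3.2 of these.

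**5. The median.** Under independence the two rules differ by at most 7.28 - 7.20 = 0.08 month. Under clustering they differ by 0.12 month or less, except at 30% with true median 6, where the median is 9.00 against 7.42 months, because Kaplan-Meier curves for scan-detected events fall in steps.

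**The case against.** The strongest reply is that 9.1.2 is only one of three TTP definitions. The qualifier in 2.4.1 and 7.1.2 can be read as confining censoring to patients with no evidence of progression. This stands: a reader might infer that the plan expressly excludes these progressions, and it does not. It is inconsistent, and the statistical section, which one would expect to govern the analysis, is the one without the qualifier.

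Other stronger inferences also fail:

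- That every patient removed for toxicity is rescanned. The scan is needed only without imaging in the preceding 8 weeks.
- That such a patient is censored at an earlier scan. Sections 2.4.1 and 9.1.2 do not tie the last progression-free date to a scan, and 7.1.2 uses discontinuation.
- That PFS discards the same events throughout. Section 7.1.2 would count them.

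On size, the shift is small beside sampling error: with N = 25 and a rate of 50%, the 95% half-width is about 1.96 × sqrt(0.25/25) = 0.196, or 20 points. Also, if the proportion in section 9.4.2 is a simple count out of 25, a patient censored before 6 months and one progressing before 6 months both fall short, so the count hardly moves. The plan does not say how censoring enters that proportion. The Kaplan-Meier estimate, which is the stated primary summary, does move.

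TTF counts toxicity removals as failures, so they stay visible, and censoring at treatment stop is a recognised on-treatment choice. That would be a defence if all sections stated it consistently; they do not. Finally, withdrawn patients may decline the scan, and section 9.4.1 allows some to be replaced, so the issue bears mainly on toxicity removals.

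**Conclusion.** The point holds as a defect in the event definition, with a modest expected effect. Read literally, 9.1.2 drops observed primary-endpoint events according to the recorded reason for removal, while other sections allow the opposite coding. Two analysts could classify the same patient differently.

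Under the assumed 10 to 30% removal parameter, about 0.4 to 3.5 progressions per 25 patients are affected. The 6-month rate under 9.1.2 exceeds the rate with the scan counted by 0.3 to 2.0 points (independent removal) or 0.7 to 3.2 points (clustered). Actual bias in 9.1.2 is close to nil under independence and upward when removal is linked to progression. These sizes depend on assumed removal rates and timing, not on figures in the documents.

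A reader might infer that the trial's conclusion or its sample size is undermined. The documents do not support that: N = 25 and the 88% power stand. Nor would counting the scan remove all bias from progression-linked removal, since the scan is conditional.

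**What to change.** Replace the differing wording in 2.4.1, 7.1.2 and 9.1.2 for TTP, and in 2.4.2, 7.1.2 and 9.1.3 for PFS, with one rule. RECIST 1.1 progression on any protocol scan up to and including the end-of-treatment scan, before new anticancer therapy, is an event at the scan date whatever the recorded reason for removal. Otherwise, censor at the last progression-free assessment. Keep the existing provisions on clinical progression and death alongside it. The rule also moves the date of on-study RECIST events from the removal date to the scan date.

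Stopping at the end-of-treatment scan is practical: later follow-up in section 6.1.6 offers "Evaluation of clinical response or deterioration" by clinic visit or telephone, and Table 6.1 schedules no imaging there.

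Record the start date of new anticancer therapy; section 6.1.6 already collects such therapies. Apply the rule to withdrawn patients only where the scan was obtained with consent. State in 9.4.2 how censored patients enter the 6-month proportion.

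The cost is one amended definition per endpoint and one date field. No added scans, visits or patients are needed.

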9.1.3 Secondary Endpoints

1. Response rate (RR) will be measured by RECIST version 1.1.

2. Median PFS will be calculated in months from date of first dose of protocol therapy to date of study removal for documented radiographic and/or clinical disease progression or death from any cause. For patients removed from study for other reasons than progression or death, PFS will be censored at the date last known to be progression-free.
3. Median OS for all enrolled patients who receive at least one dose of protocol therapy will be calculated from date of first dose of protocol therapy until date of death, using chart review and/or follow up phone calls to determine date of death in patients after removal from study. The survival of patients still alive after 5 years of follow up post study discontinuation will be censored.
4. TTF will be measured from date of first dose of protocol therapy to date of removal from study for progression, death, or toxicity. For patients removed from study for other reasons (such as noncompliance or withdrawal of consent), TTF will be censored at the date of study discontinuation.
5. In patients with baseline AFP ≥ 20 ng/mL, AFP response will be measured by the percent change from baseline value to the value at the time of best AFP response. The proportion of $\geq 50\%$ decline from baseline will be measured. The change in AFP will also be examined for association with absolute TTP and best response.
6. Toxicity will be measured using Common Terminology Criteria for Adverse Events (CTCAE) version 4.0. The frequency of dose reduction, treatment delays, and discontinuation for lack of tolerability will be quantified.

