Duration of study	The study will reach completion approximately 24 months from the time the study opens to accrual. The study will end 5 years after the final patient discontinues treatment or after all patients are deceased, whichever comes first.

Abstract

Study Drugs
	
Temsirolimus: 10 mg weekly will be administered intravenously over 30 to 60 minutes using an infusion pump starting on Cycle 1, Day 1 of study enrollment.
 
Sorafenib: 200 mg tablet twice daily starting on Cycle 1, Day 1 of study enrollment after completion of temsirolimus infusion.

Safety Assessments
	
Analyses will be performed for all patients having received at least one dose of study drug. The study will use the NCI (CTCAE) Version 4.0.

Efficacy Assessments
	
Primary Endpoint Median TTP will be calculated in months from date of first dose of protocol therapy to date of removal from study for progression; Kaplan-Meier methods will be used to summarize the primary endpoint (median TTP).
 
Secondary Endpoints Response rate (RR) will be measured by RECIST version 1.1; measurements will be presented descriptively for the study cohort.
 
Median PFS will be calculated in months from date of first dose of protocol therapy to date of documented disease progression or death from any cause. Kaplan-Meier methods will be used to summarize time-to-event outcomes including the primary endpoint (median TTP) and secondary endpoints (PFS, TTF, OS).
 
Median OS for all enrolled patients who receive at least one dose of protocol therapy will be calculated from date of first dose of protocol therapy until date of death, using chart review and/or follow up phone calls to determine date of death in patients after removal from study.
 
TTF will be measured from date of first dose of protocol therapy to date of study discontinuation for progression, death, or toxicity.
 
In patients with baseline AFP ≥ 20 ng/mL, AFP response will be measured by the percent change from baseline value to the value at the time of best AFP response. The change in AFP will also be examined for association with absolute TTP and best response.

Abstract

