2.4.2 Secondary Endpoints

- Response rate (RR) will be measured by RECIST version 1.1.
- Median PFS will be calculated in months from date of first dose of protocol therapy to date of documented disease progression or death from any cause. For patients removed from study for other reasons than progression or death, PFS will be censored at the date last known to be progression-free.
- Median OS for all enrolled patients who receive at least one dose of protocol therapy will be calculated from date of first dose of protocol therapy until date of death, using chart review and/or follow up phone calls to determine date of death in patients after removal from study.
- TTF will be measured from date of first dose of protocol therapy to date of study discontinuation for progression, death, or adverse events (related or unrelated). For patients removed from study for other reasons (such as noncompliance or withdrawal of consent), TTF will be censored at the date of study discontinuation.
- In patients with baseline AFP ≥ 20 ng/mL, AFP response will be measured by the percent change from baseline value to the value at the time of best AFP response. The proportion

of $\geq 50\%$ decline from baseline will be measured. The change in AFP will also be examined for association with absolute TTP and best response.

- Toxicity will be measured using Common Terminology Criteria for Adverse Events (CTCAE) version 4.0. The frequency of dose reduction, treatment delays, and discontinuation for lack of tolerability will be quantified.

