7.1.1.5 Centralized Review of Radiology

Radiographic assessments will be performed by a Radiologist at UCSF without knowledge of patients' clinical responses to protocol therapy for all patients' imaging studies during the first 6 months' on therapy (including imaging after completion of cycle 6). For patients enrolled on study at the Robert H. Lurie Comprehensive Cancer Center of Northwestern University, standard CT or MRI images will be acquired at that study site, stored on a CD as DICOM images, and shipped via FEDEX to the designated UCSF study coordinator. After cycle 6 imaging, RECIST 1.1 measurements may be performed at the treating site by a qualified investigator or radiologist. See Study Laboratory and Procedures Manual for detailed instructions.

Initial assessment of response or progression may be made based upon standard of care Radiology review plus clinical assessment if RECIST 1.1 measurements are not available at the time of study visit. In patients without signs of clinical progression, progression must be confirmed by RECIST 1.1 prior to removal from study. If progression is identified by RECIST 1.1 that was not identified by standard of care Radiology review plus clinical assessment, a patient will be removed from study at date of next scheduled study visit. Efforts will be made to obtain RECIST 1.1 measurements for patients treated at both sites within approximately 7 days of start of odd cycles.

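### Section 9.1.3 dates a PFS progression event at study removal, while the abstract, 2.4.2 and 7.1.2 date it at progression, and the sections disagree on whether a death after removal counts

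*Combined protocol and SAP*

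**What the plan says.** **Event date.** Four places define the PFS event.

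- Abstract, Efficacy Assessments: "date of documented disease progression or death from any cause".
- Section 2.4.2: "to date of documented disease progression or death from any cause".
- Section 7.1.2: "time of documented radiographic and/or clinical disease progression or death from any cause".
- Section 9.1.3: "date of study removal for documented radiographic and/or clinical disease progression or death from any cause".

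Only 9.1.3 brings in removal from study. Removal can come after progression. Under 7.1.1.5 (repeated in 6.1.2.2), if the RECIST reading shows progression that routine radiology and clinical assessment did not, "a patient will be removed from study at date of next scheduled study visit".

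**Censoring.** The abstract gives no PFS censoring rule. Section 2.4.2 says "For patients removed from study for other reasons than progression or death, PFS will be censored", and 9.1.3 has the same sentence. Section 7.1.2 says "Patients who have not progressed or died are censored at the date last known to be progression-free". The censoring date is the same in all three: in 2.4.2 and 9.1.3, "PFS will be censored at the date last known to be progression-free".

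**The concern.** Section 9 is where an analyst would look for the PFS rule, and it gives a different event date from the rest of the protocol. Two analysts working from different sections could assign different dates to the same progression and count different numbers of events. With 25 evaluable patients, each reclassified patient is 4% of the sample.

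The two discrepancies behave differently. Dating at removal can only move an event later, so it can only lengthen PFS. The rule on later deaths changes which patients have events. Such patients are plausible: discontinuing either drug takes a patient off study (5.2, 5.3), and survival is followed for up to 5 years afterwards (6.1.6), so the deaths would be known.

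**Working it through.** **1. The plan's own design figure.** The documents state no target, sample size or power for PFS. The only design calculation is for TTP (9.2.1): n = 25, 6-month rates of 25% against 50%, one-sided 10%, power 88%. Under an exponential model, a 3-month median gives 0.5^(6/3) = 0.25 at 6 months and a 6-month median gives 0.50. An exact binomial test that rejects at 10 or more of 25 has alpha 0.071 and power 0.885; at 9 or more, alpha is 0.149. The stated 88% reproduces, and nothing in it uses a PFS definition.

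**2. Size of the removal lag.** Inputs: from cycle 2, Table 6.1 lists visit days 1, 8, 15 and 22, with the full visit on Day 1 of each 28-day cycle. A month is 30.4375 days. Visit windows are ignored.

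- Wait to the next weekly visit: 7 / 30.4375 = 0.23 month.
- Wait to the next full visit: 28 / 30.4375 = 0.92 month.
- Removal on the progression date: 0.

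If every event carried the lag, which is an upper bound, the median would shift by the same amount. In a large-sample simulation (20,000 patients, exponential progression, scans every 8 weeks) the results were:

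| True progression median | PFS median, dated at progression | At removal, 1-week lag | At removal, 4-week lag |
|---|---|---|---|
| 3 months | 3.68 | 3.91 | 4.60 |
| 6 months | 7.36 | 7.59 | 8.28 |

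**3. Deaths after removal for another reason.** Take a patient removed for toxicity, progression-free at the last assessment, who later dies with no progression recorded.

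- Under 7.1.2 the patient has died, so the censoring sentence does not apply and the death is the event.
- Under the censoring sentence of 2.4.2 and 9.1.3, removal was for another reason, so the patient is censored at the last progression-free date. Yet the event sentence in both sections also names death from any cause.

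The documents give no removal rate and no survival after removal, so these are assumed. The same simulation was used, with no progression recorded after removal and every removed patient followed to death. Kaplan-Meier PFS at 6 months, a planned output under 9.4.3, was:

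| True median; share removed for other reasons | Later deaths censored | Counted: median 2 months from removal to death | Counted: 4 months | Counted: 8 months |
|---|---|---|---|---|
| 6 months; 33% | 0.532 | 0.470 | 0.513 | 0.551 |
| 3 months; 37% | 0.287 | 0.254 | 0.325 | 0.383 |
| 6 months; 11% | 0.528 | 0.510 | 0.524 | 0.535 |
| 3 months; 12% | 0.278 | 0.270 | 0.292 | 0.306 |

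The sign changes with survival after removal. The largest differences are 0.532 − 0.470 = 0.062 downward and 0.383 − 0.287 = 0.096 upward, or about 1.6 and 2.4 patients in 25. With 11% to 12% removed, no difference exceeds 0.306 − 0.278 = 0.028.

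**The case against.** The strongest reply is that this is a drafting slip in a descriptive endpoint. Three of the four definitions agree. The explicit wait applies only to progression found by RECIST reading alone, and 7.1.1.5 aims to have readings within about 7 days of the start of odd cycles. The next scheduled visit is nominally a week away. PFS has no hypothesis or decision rule. Its sampling error is also far larger: with 25 events and an exponential model, a 95% interval around 3.68 months is 3.68 × exp(±1.96/√25), or about 2.5 to 5.4 months. All of this stands and limits the point's importance. It does not settle which date or death rule applies.

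It can also be said that the death wording is open to interpretation. In 9.1.3, death may be a separate end date not governed by study removal, and the censoring sentence does not expressly exclude later deaths. That is fair, but progression is tied to removal on either parsing, and two defensible readings of the death rule are themselves the problem.

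Finally, counting every later death is not clearly better. Beyond the end-of-treatment assessment no imaging is scheduled (Table 6.1), and follow-up is by clinic visit or telephone every 3 to 6 months. Counting a death long after the last scan treats unobserved time as progression-free. This stands, and is why the fix includes a sensitivity analysis.

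**Conclusion.** Both inconsistencies are real and should be removed before PFS is analysed. If 9.1.3 is followed, PFS is lengthened for patients whose progression only the RECIST reading finds: about 0.23 month with weekly visits and at most 0.92 month for a wait to the next 28-day full visit, on the nominal schedule. The death rule changes who has an event, with no fixed direction; its size above rests on assumed removal rates and survival. The TTP sample size and power are not touched.

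A reader might infer four stronger things that the documents do not support.

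- That PFS is inflated. This holds only if 9.1.3 governs, only for patients with a lag, and not for the death rule, which can move PFS either way.
- That 2.4.2 and 9.1.3 censor PFS at removal. Removal is the trigger; the censoring date is the last progression-free date, as in 7.1.2.
- That a 28-day delay is typical. It is a ceiling: Table 6.1 has weekly visits, and the lag may be zero.
- That comparison with published benchmarks is lost. The benchmarks in 9.2.1 are for TTP, and no PFS comparison is planned.

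**What to change.** - **Event date.** In 9.1.3, drop the reference to study removal. End PFS at the scan or clinical assessment that first documents progression, or at the date of death, matching 2.4.2 and 7.1.2. The removal procedure itself need not change.
- **Death and censoring rule.** Use one rule in 2.4.2, 7.1.2 and 9.1.3. The 7.1.2 rule is a reasonable choice: a death without prior progression is an event whether or not the patient has left the study, and everyone else is censored at the last progression-free assessment. State how progression first reported during follow-up is handled.
- **Sensitivity analysis.** Repeat PFS with deaths after removal censored at the last progression-free assessment, because no imaging is scheduled in follow-up.

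The cost is wording and one extra analysis, with no new patients or visits. PFS may come out slightly shorter from the re-dating. TTP is also dated at removal in its own definitions, so the same progression could carry different dates for TTP and PFS; the report should say so.
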